#### 18. EFFICACY OUTCOMES

#### 18.1. PRIMARY EFFICACY

#### 18.1.1. PRIMARY EFFICACY VARIABLE & DERIVATION

The primary efficacy variable is the change in the AAPS from baseline to Week 12, where baseline is based on the randomization date (Day 1). Baseline AAPS and AAPS by week during the treatment period is derived as described in Section 7.2. Baseline AAPS is a required datapoint for eligibility; therefore, no missing data for baseline AAPS is expected. For the treatment period, if any AAPS value is completely missing, the primary efficacy analysis will be conducted on the non-missing data.

#### 18.1.2. MISSING DATA METHODS FOR PRIMARY EFFICACY VARIABLE

Missing AAPS will not be imputed for the primary analysis. The primary analysis method, MMRM, will utilize all data available during the Main Study treatment period from subjects included in the FAS. Analysis of sensitivity to missing data for the primary endpoint will be performed as described in Section 18.1.4.

#### 18.1.3. PRIMARY ANALYSIS OF PRIMARY EFFICACY VARIABLE

The primary efficacy analysis will be performed using the FAS population. The primary efficacy endpoint will be analyzed using a MMRM analysis with treatment group (placebo, olorinab 10 mg, olorinab 25 mg, olorinab 50 mg), stratification factors (sex and IBS subtype), week, and treatment-by-week interaction as factors and baseline AAPS as a covariate. Week will include each week from Week 1 to Week 12 based on eDiary data beginning from Day 1 (Randomization). In addition, two additional MMRMs will be completed with the following treatment groupings: 1) placebo, olorinab 10 mg, and olorinab 25 and 50 mg pooled and 2) placebo and pooled olorinab.

The primary objective of this study is to test the hypothesis that the change in AAPS from baseline to Week 12 is the same across treatment group (placebo, olorinab 10 mg, 25 mg, and 50 mg). The alternative hypothesis is that the change in AAPS from baseline to Week 12 differs between placebo and one of the olorinab treatments (10 mg, 25 mg, or 50 mg) or olorinab 25 mg/50 mg pooled.

Four hypothesis tests for the primary endpoint using the primary analysis methodology

described above are specified below.

- MMRM model with treatment groups (placebo, 10 mg, 25 mg, and 50 mg), and with
   3 pre-specified comparisons of placebo vs. the individual treatment groups of olorinab (10 mg, 25 mg, and 50 mg)
- MMRM with treatment "groups" placebo, 10 mg, and pooled olorinab [25 mg + 50 mg], and with 1 pre-specified comparison of placebo vs. the pooled olorinab group [25 mg + 50 mg]

No multiplicity control is planned for this Phase 2 study. If any of the four pre-specified hypothesis test analyses demonstrates statistical significance at the 0.05 (2-sided) significance level at Week 12, then the study successfully demonstrated that the primary endpoint was met.

Change from baseline to Week 12 by scheduled visit is considered the supporting primary efficacy endpoint. It will be analyzed using a model of MMRM with treatment (placebo, olorinab 10 mg, olorinab 25 mg, olorinab 50 mg), stratification factors (sex and IBS subtype), visit, and treatment-by-visit interaction as factors and baseline AAPS as a covariate. Visits will include all scheduled visits except Visit 9 (Week 14). The analysis will also be repeated using the treatment groupings described in the preceding paragraph. If one of the MMRM models demonstrates statistically significant difference between placebo and one of the active doses of olorinab at Week 12, olorinab may be declared to achieve a statistically better reduction in AAPS than placebo.

All models will be run under the assumption of an unstructured covariance matrix. If the unstructured covariance matrix results in a lack of convergence, the heterogeneous Toeplitz covariance structure, followed by the heterogeneous autoregressive covariance structure, followed by compound symmetry will be used. The Newton-Raphson with ridging optimization technique will be used to aid with convergence. The Kenward-Rogers method will be used to estimate the denominator degrees of freedom. An example of the SAS PROC MIXED code used for the repeated measures models is provided in Appendix 4. Example SAS Code.

Descriptive statistics, including the number of observations, mean, SD, median, minimum, and maximum will be provided by treatment at each scheduled visit or each week. Additionally, p-values for within-treatment group change (for the primary efficacy variable, change in AAPS from baseline to Week 12) resulting from a one sample t-test using least squares mean estimates and associated standard errors will be presented by treatment. Least square mean differences between treatment groups ([i.e., olorinab 10 mg vs. placebo,

olorinab 25 mg vs. placebo, and olorinab 50 mg vs. placebo], [olorinab pooled vs. placebo] or [olorinab 10 mg vs. placebo, olorinab 25 and 50 mg pooled vs. placebo]), the corresponding standard errors, 95% CIs, and p-values will also be presented.

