# 3.2. Scientific Rationale for Study Design

IBS is a GI disorder characterized by abdominal pain associated with defecation or change in bowel habits (Lacy 2016). Symptoms are chronic and may be episodic in nature, varying widely among patients (Miller 2014, Weinland 2011). In clinical studies of IBS, a run-in period of 1-3 weeks is recommended to monitor presence and consistency of symptoms according to study entry criteria (EMA 2014, FDA 2012, Miller 2014, Spiegel 2017). Accordingly, this study will incorporate a Main Study Run-in Period of at least 2 weeks (14-19 days), which will be used to

<sup>a Gap subjects start the LTE at Visit 1.

<sup>b Continuing subjects start the LTE at Visit 2.

train subjects on the proper completion of patient-reported outcome (PRO) instruments, to confirm subject eligibility with respect to abdominal pain severity, and to establish baseline values of various assessments.

Based on its mechanism of action as a selective CB2 agonist and data from previous nonclinical and clinical studies, it is anticipated that olorinab may have an effect on abdominal pain in patients with IBS, but will not have an effect on motility or bowel symptoms of constipation or diarrhea (Mathison 2004). Per FDA Guidance for Industry, Irritable bowel syndrome - clinical evaluation of drugs for treatment (FDA 2012), abdominal pain score (APS) is the recommended instrument for measuring pain in IBS. The instrument is a patient-reported outcome that uses an 11-point numeric rating scale ranging from 0 (no abdominal pain) to 10 (worst possible abdominal pain). The scale has been validated and has been widely used in clinical studies on pain in IBS (Spiegel 2009). Subjects in this study will record their worst abdominal pain over the previous 24 hours in a daily electronic diary (eDiary). Abdominal pain in IBS can fluctuate daily. To better capture a summary of subject pain, the AAPS (for Baseline: the average of all APS scores during the Run-In Period; for post-baseline visits: the average of the APS score over the 7 days before the scheduled visit) will be used to summarize subject pain and compare changes in pain over time. In the absence of significant safety findings, a greater decrease in AAPS in olorinab-treated subjects compared to placebo-treated subjects over the course of this study will provide supportive evidence that olorinab provides a direct benefit to subjects.

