# 8.7. Testing Strategy/Multiplicity

No formal testing strategy or adjustments of the type I error will be employed for the primary, secondary or exploratory endpoints. Estimates and CIs for treatment groups and from pairwise comparisons will be used in an exploratory manner.

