#### 9.4. MULTIPLE COMPARISONS/ MULTIPLICITY

No formal testing strategy or adjustments of the type I error will be employed for the primary, secondary or exploratory endpoints. Estimates and CIs for treatment groups and from pairwise comparisons will be used in an exploratory manner.

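### The SAP declares the primary endpoint met if any of four unadjusted tests is significant in either direction, while SAP 9.4 and protocol 8.7 promise only exploratory reading

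*SAP*

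**What the plan says.** Main Study SAP 18.1.3 lists "Four hypothesis tests for the primary endpoint using the primary analysis methodology". Three compare 10, 25 and 50 mg with placebo in the four-group by-week MMRM. The fourth compares pooled 25+50 mg with placebo in a three-group version of that model. The section states "No multiplicity control is planned for this Phase 2 study", and then gives the consequence of any one of the four (the word any is underlined) showing "statistical significance at the 0.05 (2-sided) significance level at Week 12, then the study successfully demonstrated that the primary endpoint was met".

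The hypothesis is worded without direction: "The alternative hypothesis is that the change in AAPS from baseline to Week 12 differs between placebo and one of the olorinab treatments", with the pooled 25+50 mg group as a further option.

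The next paragraph turns to the by-visit model: "Change from baseline to Week 12 by scheduled visit is considered the supporting primary efficacy endpoint". It carries its own declaration: a significant difference from placebo for one active dose allows olorinab to be called better at reducing AAPS. That condition has no direction either.

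Elsewhere the plan reads differently. Protocol 8.7 says: "No formal testing strategy or adjustments of the type I error will be employed for the primary, secondary or exploratory endpoints". SAP 9.4 repeats this and adds: "Estimates and CIs for treatment groups and from pairwise comparisons will be used in an exploratory manner". Protocol 3.2 does say which direction is of interest: "a greater decrease in AAPS in olorinab-treated subjects compared to placebo-treated subjects".

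**The concern.** A rule that turns any one significant result into a statement that the primary endpoint was met is a decision rule with a pass/fail outcome. SAP 9.4 and protocol 8.7 describe a trial without one. An author of the clinical study report cannot follow both: one section licenses a headline claim, the other says comparisons are exploratory.

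Two features make the claim hard to interpret. It can rest on one of four unadjusted tests, and the SAP does not say how often that happens when the drug does nothing. And because no direction is required, the words are satisfied by a dose on which pain improved significantly less than on placebo.

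**Working it through.** **Inputs.** SAP 8 and protocol 8.1: four arms of 60, SD 1.9, difference 1.0, two-sided 0.05. SAP 18.1.3: four tests, no adjustment, success if any is significant. The documents give no overall error rate for the rule, so the only related design figure that can be reproduced is per-dose power.

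**Reproducing the plan's figure.** Standard error = 1.9 × √(2/60) = 0.347, and 1.0/0.347 = 2.88. Normal approximation: Φ(2.88 − 1.96) = 82.2%. Noncentral t gives 81.6% with 118 df and 81.9% with 236 df. The stated minimum of 80% is confirmed.

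**Correlation between the tests.** All four share the placebo arm. In units of σ²/n:
- A single-dose difference has variance 1 + 1 = 2. Two such differences share covariance 1, so r = 1/2 = 0.5.
- The pooled 25+50 mg difference has variance 1/2 + 1 = 1.5.
- Pooled with 25 or 50 mg: covariance 1/2 + 1 = 1.5, so r = 1.5/√(2 × 1.5) = 0.866.
- Pooled with 10 mg: covariance 1, so r = 1/√(2 × 1.5) = 0.577.

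Treating the tests as independent would give 1 − 0.975⁴ = 9.6% (favourable) and 1 − 0.95⁴ = 18.5% (either direction). Both are too high, so the correlated case was simulated. The single-dose tests used 240 − 4 = 236 df and the pooled test, in its own three-group model, 240 − 3 = 237 df.

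**No effect in any arm (4,000,000 trials at 60 per arm).**

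| Rule | Favours olorinab | Either direction |
|---|---|---|
| One test | 2.5% | 5% |
| Three single doses | 6.3% | 12.5% |
| All four tests (SAP rule) | 6.5% | 13.0% |
| All four, 48 per arm (assumed 20% loss) | 6.5% | 13.0% |

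The pooled test adds about 0.25 points to the favourable figure. As a cross-check, the exact multivariate normal value for three favourable single-dose tests is 6.27%.

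**With true effects (2,000,000 trials each).** Chance that the rule is met:

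| Effect at 10, 25, 50 mg | Either direction | Favourable only |
|---|---|---|
| 1, 1, 1 | 96.2% | 96.2% |
| 0, 1, 1 | 94.5% | 93.6% |
| 0, 0, 1 | 84.6% | 82.0% |

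In the last row the difference of 84.6 − 82.0 = 2.6 points consists of trials in which the only significant result was in the wrong direction. Requiring direction removes no trial that had a significant result favouring olorinab.

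**An adjusted threshold, for comparison.** Holding the four tests to 5% overall needs a critical value of about 2.37, or p below about 0.018 per test. Per-dose power would fall from 82% to 68–69%.

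**The case against.** The strongest reply is that this is an openly unadjusted Phase 2 trial. The SAP says so in the sentence before the rule. Testing was always planned: protocol 8.1 powers each dose at two-sided 0.05, protocol 8.3 and Table 6 call for p-values, and SAP 7.5 sets a 5% default level. Three of the four comparisons were already in the protocol and by themselves give 6.3%, so the SAP's choice of tests created little of the error. A two-sided alternative worded as a difference is conventional. The stated objective is improvement in pain, and signed differences with intervals are reported, so a harmful result could not be hidden. The Main Study analysis is also complete.

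Much of this stands. Unadjusted testing is not the fault, the p-values are compatible with protocol 8.7, and the 13.0% belongs to a literal reading that a sensible author would probably not use. But disclosing that tests are unadjusted does not disclose the error rate of a combined success claim, and the protocol's p-values carry no success rule. What SAP 18.1.3 adds is the formal consequence of a positive test, and SAP 9.4 does not mention it. If direction was intended, writing it down costs nothing. Completion of the analysis changes where the correction goes, not whether it is needed.

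**Conclusion.** The concern holds and should be fixed. The declaration that the primary endpoint was met is inconsistent with SAP 9.4 and protocol 8.7, lacks a direction and has no stated error rate. With no effect in any arm, it would be triggered by a result favouring olorinab 6.5% of the time against 2.5% for one test, and 13.0% against 5% if taken literally.

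These rates assume equal arms, common variance, normal Week 12 means and no differential missing data, with simple group comparisons standing in for the MMRM. Under the null they do not depend on the SD. They cover only the four by-week tests. Any further error from the separate by-visit declaration cannot be computed from the documents.

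A documentation point from the same section adds no weight. SAP 4.3 reports no changes from the protocol, yet protocol Table 6 makes the by-visit model primary and the by-week model an additional one. SAP 18.1.3 reverses those roles and adds the pooled 25+50 mg comparison and the success rule.

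**What to change.** LTE SAP 4.3 shows that the Main Study analysis is finished, so the correction belongs in the clinical study report, with the SAP left as the pre-specified record. Either:

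1. Drop both declarations and report the Week 12 differences as estimates with confidence intervals, as SAP 9.4 and protocol 8.7 describe. This gives up the only written Main Study success criterion in the documents shown.
2. Keep one statement, tied to the by-week model, that requires the difference to favour olorinab and gives its error rate. For example: *At least one of four unadjusted comparisons favoured olorinab at two-sided p<0.05; with no effect in any group this occurs about 6.5% of the time.* The report should note that SAP 9.4 does not mention this rule; before unblinding, SAP 9.4 itself should have been amended. The 6.5% remains but is visible.

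Under either option, record against SAP 4.3 that the primary model moved from by-visit to by-week and that the pooled 25+50 mg comparison and the success rule were added.

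The cost is a few sentences and no new analysis. A multiplicity-adjusted threshold is not recommended: it trades away power, as shown above, and would now be post hoc.

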#### 18.1.4. SENSITIVITY ANALYSIS OF PRIMARY EFFICACY VARIABLE

The robustness of the primary endpoint result will be assessed for the FAS using various sensitivity analyses. The following analyses will be used:

- ANCOVA with observed cases (OC): Treatment comparisons of the change in the AAPS from baseline to Week 12 will be made using an ANCOVA model with treatment and stratifications (sex and IBS subtype) as factors and baseline AAPS as a covariate. Type III sums of squares for least-squares (LS) will be used for the statistical comparison; the least squares mean differences, 95% CI, and p-value for each least squares mean difference value will be reported.
- ANCOVA with multiple imputation (MI): MI under the missing at random (MAR) assumption will be performed. Any missing AAPS data from Week 1 to Week 12 at the planned assessments will be imputed using MI under MAR. MAR assumes the missing value is independent of unobserved outcomes given observed data (i.e., subjects with missing AAPS can be modeled based on subjects with observed AAPS). Unscheduled visits are not included in the analysis for this approach. The following steps will be implemented:
  - ✓ Step 1: Non-monotone missing data will first be imputed to a monotone missing pattern using the multivariate joint Gaussian imputation model that utilizes the Markov Chain Monte Carlo (MCMC) method in the SAS PROC MI procedure. The number of imputations will be 100 and SEED = 4161. Each imputed dataset will only have missing data at the end of subjects' records (monotone missing data pattern). A separate imputation model will be used for each treatment group and only subjects with non-missing baseline AAPS will be included. If convergence cannot be met using a separate imputation model for each treatment group, data for all treatments will be imputed using the same model. The stratification variables at each planned visit will be included in the imputation models.
  - ✓ Step 2: The remaining monotone missing data will be imputed using sequential regression MI, where a separate regression model is estimated for the imputation of each variable (i.e. measurement at each time point). Each regression model will include explanatory variables for treatment, baseline AAPS, and the stratification factors. The number of imputations will be 1 and SEED = 4161.
  - ✓ Step 3: An ANCOVA model with treatment, randomization stratification (sex and

- IBS subtype) as factors and baseline AAPS as a covariate will be run for each of the 100 datasets to obtain 100 estimators of interest.
- ✓ Step 4: SAS PROC MIANALYZE will be used to produce overall pooled estimates (mean of 100 estimates) of least squares mean differences between placebo and each treatment with associated standard errors, CIs, and pooled p-values presented. Additionally, SAS PROC MIANALYZE will be used to produce p-values for within-treatment group change based on a one sample t-test using pooled least squares mean estimates and associated standard errors. Summary statistics presented for Week 12 records will be based on the mean of the imputed records per subject per time point.

The missing AAPS values will be imputed first and change from baseline values will be calculated based on imputed AAPS scores.

There could be certain adjustments to the MI model specified in Step 2 above due to unexpected data issues after unblinding treatment. All post-unblinding modifications to the MI model or approaches to address missing data will be described in the Clinical Study Report (CSR).

• Nonparametric Wilcoxon Rank-Sum Test: The Wilcoxon Rank-Sum Test will be used to compare change in AAPS at Week 12 between treatment (each dose of olorinab vs placebo, olorinab 25 and 50 mg pooled versus placebo, and pooled olorinab vs placebo).

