#### **5.2.** FINAL ANALYSIS

All final, planned analyses identified in this SAP will be performed following Sponsor Authorization of this SAP, Database Lock, Sponsor Authorization of Analysis Sets and Unblinding of Treatment. PK analysis will be performed and is described in this analysis plan.

After all subjects have completed the Main Study, outstanding data queries have been resolved/closed, and the data have been cleaned and finalized, the Sponsor will authorize breaking of the study blind and the final analysis of the data will be performed. The SAP must be approved and signed by the Sponsor before the database is locked and treatment assignment unblinded.

Any post-hoc, exploratory analyses completed to support planned study analyses, which were not identified in the SAP, will be documented and reported in the clinical study report. Any results from these unplanned analyses will also be clearly identified in the text of the clinical study report.

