#### 18.2.2. MISSING DATA METHODS FOR SECONDARY EFFICACY VARIABLES

For the continuous endpoint of percent change in AAPS from baseline to Week 12, the MMRM models described in Section 18.1.3 will be used. For the continuous endpoint of change in number of pain free days per week from baseline to Week 12, the by-week MMRM model described in Section 18.1.3 will be used. For the change in number of pain free days per week endpoint, a subject with a missing value for a given day when there are non-missing values during the week will be assumed to not be pain free for that day.

For the binary endpoints of proportion of subjects achieving a  $\geq$  30% improvement in AAPS from baseline to Week 12 and proportion of subjects achieving a  $\geq$  30% improvement in AAPS from baseline for at least 6 of the 12 weeks during the Main Study treatment period, all missing post-baseline AAPS values will be imputed using MI under the MAR assumption as described in Steps 1 and 2 of Section 18.1.4. The following steps will then follow:

- Step 3: Subjects will be classified as responders or non-responders per imputed data based on the endpoint criteria specified in Section 18.2.1 for the endpoint of interest. For each dataset, the proportion of responders and non-responders will be calculated.
- Step 4: The Cochran-Mantel-Haenszel (CMH) test, stratified by sex and IBS subtype, will be run for each of the 100 datasets to obtain 100 odds ratio estimates of interest (active treatment over placebo). Common risk difference estimates, CIs, and two-sided p-values will also be calculated for active treatment minus placebo based on

Mantel-Haenszel weights. For the 100 odds ratio estimates and difference estimates in each treatment, the estimates will be passed directly to PROC MIANALYZE, along with their associated standard errors. In some cases, an odds ratio estimate may be calculated as missing due to a value of zero in the denominator for certain treatment comparisons; the missing value for that imputation cannot be passed to PROC MIANALYZE. As a result there may be fewer than 100 odds ratio estimates used to calculate the pooled estimate in these instances.

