 Step 5: SAS PROC MIANALYZE will be used to produce an overall pooled estimate (mean of 100 estimates) of the odds ratio with associated CI, and of the percentage difference estimate with associated standard error, CI, and two-sided pooled p-values. Counts and percentages of responders will also be summarized using SAS PROC MIANALYZE.

The MI model will be pre-defined before database lock. However, there could be certain adjustments due to unexpected data issues after unblinding treatment. All post-unblinding modifications to the MI model or approaches to address missing data will be described in the CSR.

The robustness of the secondary endpoint results will be assessed using various sensitivity analyses, described in Section 18.2.4.

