#### 18.2.3. ANALYSIS OF SECONDARY EFFICACY VARIABLES

For the continuous secondary efficacy endpoints, percent change in AAPS from baseline to Week 12 and change in number of pain free days per week from baseline to Week 12, the same methodology used for the primary efficacy endpoint will be used for the analysis. The analyses for percent change in AAPS from baseline at Week 12 will include both evaluation at the scheduled visit for Week 12 (Visit 8) and Week 12 based on baseline day as described in Section 18.1.3. The analyses for change in number of pain free days per week from baseline at Week 12 above will include the evaluation at Week 12 based on baseline day as described in Section 18.1.3.

For the binary secondary efficacy endpoints (proportion of subjects with a  $\geq$  30%,  $\geq$  40%, and  $\geq$  50% improvement in AAPS from baseline to Week 12 and proportion of subjects achieving a  $\geq$  30%,  $\geq$  40%, and  $\geq$  50% improvement in AAPS from baseline for at least 6 of the 12 weeks during the Main Study Treatment Period), a CMH test will be conducted to compare placebo against each of the olorinab treatments (10 mg, 25 mg, 50 mg, pooled 25 and 50 mg, and olorinab pooled), stratified by the randomization factor (sex and IBS

subtype). The responder rate and the odds ratio relative to placebo will be presented with corresponding CIs, and the percentage of difference from placebo will be presented together with corresponding 95% CIs and the p-values. The 95% CI for the responder rate of each treatment group will be generated using the normal approximation method. Missing data will be imputed using MI, as described in Section 18.2.2.

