## 18.2.4. SENSITIVITY ANALYSIS OF SECONDARY AND KEY EXPLORATORY EFFICACY VARIABLES

The robustness of the secondary endpoints' results will be assessed using various sensitivity analyses. The following analyses will be used:

- For continuous endpoints, the ANCOVA with OC, ANCOVA with MI, and Non-parametric Wilcoxon Rank-Sum Test will be implemented as described in Section 18.1.4.
- For binary endpoints based on AAPS and bowel motility endpoints (including the three composite responder endpoints for IBS-C and IBS-D), the sensitivity to missing data assumptions will be evaluated with the following models:
  - CMH with OC: The CMH test described in the analysis of secondary efficacy variables Section will be repeated on the population of subjects with observed data for the given analysis.
  - o CMH with NRI (non-responder imputation): The CMH test described in the analysis of secondary efficacy analysis Section will be completed on all subjects in the FAS. Subjects will be considered a non-responder if they do not meet the endpoint criteria (e.g. a ≥ 30% improvement in AAPS) or are missing data at the time point of interest. All non-responders at the time point of interest, as well as subjects who discontinue study treatment at any time prior to that time point for any reason, will be defined as non-responders for the analysis. Randomized subjects without at least 1 post-baseline observation will also be defined as non-responders in NRI analyses.
  - o Logistic regression (OC): A logistic regression model using observed cases will be used to analyze treatment comparisons between the proportion of subjects achieving a ≥ 30% improvement in AAPS from baseline to the given time point, with the explanatory variable of treatment (placebo, olorinab 10 mg, olorinab 25 mg, olorinab 50 mg), randomization stratification factor (sex and IBS subtype) and baseline AAPS as a covariate. In addition, two additional logistic regression models will be completed with the following treatment groupings: 1) placebo, olorinab 10 mg, and olorinab 25 and 50 mg pooled and 2) placebo and pooled olorinab. The endpoint of subjects

[figure not shown]

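### SAP 18.2.2 lets the imputation model behind the six secondary responder analyses be changed after unblinding, on an undefined trigger

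*SAP*

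**What the plan says.** SAP 18.2.2 covers missing data for the secondary endpoints. For the two responder endpoints at the 30% threshold it states that "all missing post-baseline AAPS values will be imputed using MI under the MAR assumption as described in Steps 1 and 2 of Section 18.1.4". SAP 18.2.3 then describes the stratified CMH test for all six secondary responder endpoints (30%, 40% and 50% improvement, each at Week 12 and for at least 6 of 12 weeks) and says "Missing data will be imputed using MI, as described in Section 18.2.2". So MI followed by CMH is the main analysis of all six.

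On timing, SAP 18.2.2 first says "The MI model will be pre-defined before database lock". The next sentence qualifies it: "However, there could be certain adjustments due to unexpected data issues after unblinding treatment".

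SAP 18.1.4, where MI is a sensitivity analysis of the primary endpoint, carries the parallel sentence: "There could be certain adjustments to the MI model specified in Step 2 above due to unexpected data issues after unblinding treatment". Both sections say that modifications made after unblinding will be described in the clinical study report, and both extend this to the approaches used for missing data generally.

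SAP 5.2 sets the general rule: "The SAP must be approved and signed by the Sponsor before the database is locked and treatment assignment unblinded". Protocol 8.3 likewise has the Main Study SAP final before lock, which it equates with unblinding.

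**The concern.** An imputation model decides which subjects with missing Week 12 diaries count as responders. If it may be altered once the arm codes are open, the responder difference can depend on a choice made with knowledge of treatment. The report would say that a change was made. It would not show whether the change was needed, or what the planned model would have given. The plan says in SAP 9.4 that estimates and confidence intervals are to be read in an exploratory manner, and those are the quantities that such a change moves.

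**Working it through.** **1. Which results depend on the MI model**

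- Primary endpoint, main analysis (SAP 18.1.2 and 18.1.3): a mixed model for repeated measures with no imputation. Not affected.
- Primary endpoint, ANCOVA with MI (SAP 18.1.4): a sensitivity analysis. Affected through Step 2.
- Six secondary responder endpoints, main CMH analysis (SAP 18.2.2 and 18.2.3): affected. The permission here is not confined to Step 2.
- The same endpoints analysed by CMH on observed cases, CMH with non-responder imputation, and logistic regression on observed cases (SAP 18.2.4): these do not use the MI model, but they are sensitivity analyses only.
- Exploratory responder endpoints: their main analysis is not visible in the public text, so it cannot be checked.

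**2. How this sits with the rest of the plan**

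Other choices are closed before unblinding or have a stated order of retreat. Analysis sets are agreed before unblinding (SAP 6). The covariance structures for the mixed model are ranked (SAP 18.1.3). Step 1 of the imputation says what to do if separate models by arm do not converge (SAP 18.1.4). Step 2 has no such order. The visible text also does not define the triggering problem, require a blinded decision-maker, or require the planned MI result to be shown beside the changed one.

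**3. Illustration of size**

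From the plan (SAP 8): 60 subjects per arm and SD of change 1.9. As a check on these inputs, the t-test power for 60 against 60, difference 1.0, two-sided 5%, is 81.6%, which agrees with the stated 80% or more. The present point does not rest on that figure.

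Assumed, because the documents give no value: baseline mean 6, SD 1.2, limited to 4–10; mean change at Week 12 of −2 in both arms (no treatment effect); an earlier week with mean change −1.5, SD 1.6, correlated 0.7 with Week 12; Week 12 values removed at random with probability 10%, 20% or 30%; 50 imputations; 4,000 simulated trials; unstratified risk difference.

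A subject is a responder if Week 12 AAPS ≤ 0.7 × baseline. For each imputed data set, d = p₁ − p₀ and u = [p₁(1 − p₁) + p₀(1 − p₀)]/60. The pooled variance is T = mean(u) + (1 + 1/50) × B, where B is the variance of d between imputations.

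Four imputation models were compared: (a) treatment and baseline; (b) those plus the earlier week; (c) baseline and earlier week without treatment; (d) baseline and earlier week, fitted separately by arm. The spread is the largest minus the smallest pooled d in each trial.

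| Missing | Mean spread (points) | 95th percentile (points) | Type I error, one fixed model (a, b or d) | Type I error, smallest p of four |
|---|---|---|---|---|
| 10% | 1.8 | 4.0 | 4.4–4.7% | 5.5% |
| 20% | 2.9 | 6.1 | 4.3–4.4% | 5.8% |
| 30% | 3.9 | 8.0 | about 3.6% | 5.1% |

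For scale, with 60 per arm and response near 50%, the standard error of the difference is √(2 × 0.5 × 0.5/60) = 0.091, or 9.1 points. The 95th-percentile spread at 30% missing is therefore 8.0/9.1 = 0.88 of a standard error, and the mean spread is 3.9/9.1 = 0.43.

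Two cautions apply. The simulation error on a 5% rejection rate is √(0.05 × 0.95/4000) = 0.34 points, so the last column is barely distinguishable from 5%. Each model also used its own imputation draws, so the spread includes some simulation noise as well as the effect of model choice.

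**The case against.** The strongest reply is that this is an exploratory Phase 2 trial with no type I error control (SAP 9.4), that the SAP promises to disclose any change, and that the observed-case and non-responder analyses are fixed and do not use the MI model. SAP 5.2 also requires analyses not identified in the SAP to be clearly identified as such in the report. Some fitting failures could appear only with the true arm codes, because Step 1 fits a model per arm. And the wording refers to the time after unblinding; it does not say that anyone would have seen results by arm.

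Much of this stands, and it keeps the point moderate. It does not remove it. A change that the SAP itself allows need not count as unplanned, so the labelling rule in SAP 5.2 may not bite. The fixed observed-case and non-responder analyses give a reader something to compare with, but they rest on different assumptions about missing data and do not show what the planned MI model would have given. The arm-specific fitting risk lies in Step 1, which already has its fallback; Step 2 as written is a small regression on treatment, baseline and the stratification factors.

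A reader might go further and infer that the primary result is open to adjustment, or that every responder endpoint is affected. The documents do not support either. The primary mixed model imputes nothing, the sentence in SAP 18.1.4 concerns a sensitivity analysis, and only the six secondary responder endpoints can be verified.

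**Conclusion.** The concern holds for the main analysis of the six secondary responder endpoints and for the MI sensitivity analysis of the primary endpoint. The permission undercuts the plan's own rule that the SAP is final before lock and unblinding. Description in the study report is the only safeguard specific to these changes.

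The likely size is a few percentage points on the responder difference: about 2 to 4 on average and 4 to 8 at the 95th percentile, for 10% to 30% missing. This is illustrative. It rests on an assumed baseline, correlation and missingness mechanism, and on four models chosen as plausible. It does not bound what an unrestricted change could do.

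A reader might also infer serious inflation of false positives. The calculation does not show that: picking the best of four models gave 5.1% to 5.8%. The case rests on movement of the estimate and on credibility. It merits correction, but it does not threaten the trial's primary conclusion.

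**What to change.** Remove the permission sentence in SAP 18.1.4 and in SAP 18.2.2. Keep the sentence in each that commits to describing changes in the study report.

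Before unblinding, write out the Step 2 model in full and give a fallback order for fits that cannot be estimated, as Step 1 already does for convergence. The fallbacks must differ from the present Step 2 model, which already includes treatment as a covariate. An example is a ridge prior, then fewer weeks in the imputation; the dry run should confirm that the chosen software supports each. Test the code on the blinded data with dummy treatment codes.

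If the true arm codes still force a change, report the pre-specified MI result wherever it can be estimated, together with the pre-specified observed-case and non-responder results, and label the changed version post hoc.

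The cost is a little SAP wording and one blinded dry run. The dry run may not reveal every failure specific to the true arms, which is why the reporting rule is needed as well.
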